2. STUDY OBJECTIVES

2.1. Primary Objective

The primary objective of the study is to demonstrate the reduction of LDL-C by evinacumab 15 mg/kg IV in comparison to placebo after 24 weeks in patients with HoFH.

2.2. Secondary Objective(s)

The secondary objectives of the study are:

- To evaluate the effect of evinacumab 15 mg/kg IV on other lipid parameters (ie, Apo B, non-HDL-C, total cholesterol [TC]) in patients with HoFH
- To evaluate the effect of evinacumab on LDL-C goal attainment
- To assess the effect of evinacumab on eligibility for apheresis (using German and US apheresis criteria)
- To evaluate the safety and tolerability of evinacumab 15 mg/kg in patients with HoFH
- To determine concentrations of evinacumab in patients with HoFH
- To evaluate the potential development of anti-evinacumab antibodies

2.3. Other Objective

- Genotyping will be performed for all patients to identify mutations causing HoFH and to characterize LDLR function, in order to explore potential differences in efficacy and safety.
- To assess the effect of evinacumab on quality of life using the EQ-5D and HADS QOL questionnaires

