4.2.4. Other Endpoints

- The change in hemoglobin A1c (HbA1c [%]) from baseline to week 24
- Response of each EQ-5D item, index score, and change of index score from baseline through week 24
- Response on Hospital Anxiety and Depression Scale (HADS) from baseline through week 48.

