3.6. Quality-of-life Analysis Set

The analyses for quality of life in the respective treatment period (DBTP and OLTP) will be performed on all randomized patients who received any study treatment with a baseline and at least 1 post-baseline evaluation. Further for each scale:

- For EQ-5D, patients will be included when at least 1 post-baseline utility score is available.

- For HADS, patients will be included for each sub-scale (anxiety and depression) when at least 1 post-baseline sub-scale is available, and included for the total score when at least one post-baseline total score is available.

Treatment assignments for the DBTP are based on the treatment received (placebo or evinacumab).

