4.12. Quality-of-Life Variables

EQ-5D

EQ-5D is a standardized and generic instrument for measuring the health status and health related quality of life for clinical and economic assessment (Dolan 1997). The EQ-5D instrument includes 5 items corresponding to the following dimensions: mobility, self-care, usual activities, pain/discomfort, and anxiety/depression. Each item can take one of three responses: (1.) “no problem”, (2.) “some problems”, and (3.) “severe problems”. Overall health state is defined as a 5-digit number and will be converted into a standard utility score ranging between - 0.594 (representing severe problems) and 1 (representing no problem): the single index utility score, using a regression model (Dolan 1997) (Appendix 10.5). If response to one or more dimensions is missing, the utility score will be missing.

Quality of life endpoints include response to each EQ-5D items at week 0 and week 24. The change in utility score from baseline will also be evaluated at each post-baseline week. Protocol schedule visits will be assigned to the Global Analysis Windows (See Appendix 10.2).

Hospital Anxiety and Depression Scale (HADS)

HADS is a validated, widely used questionnaire designed to identify anxiety disorders and depression in patients at non-psychiatric medical institutions. Repeated administration also provides information about changes in a patient’s emotional state (Bjelland 2002, Herrmann 1997, Zigmond 1983). The HADS questionnaire consists of 14 items that assess symptoms experienced in the previous week, with 7 items that are related to anxiety and 7 that are related to depression (See Appendix 10.6 for the details). Patients provided responses to each item based on a 4-point Likert scale. Each item on the questionnaire is scored from 0 (the best) to 3 (the worst); thus, a person can score between 0 and 21 for each subscale (anxiety and depression). A high score is indicative of a poor state. Scores of 8 or more on the HADS-Anxiety or the HADS-Depression subscale are considered to be indicative of anxiety or depression, respectively (Bjelland 2002).

The HADS total score is the sum of the two sub-scores, anxiety and depression. In the case a sub-score is missing, the HADS total score is considered missing. Similarly, in the case questionnaire items are missing, the applicable sub-score is considered also missing.

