5.12. Analysis of Quality-of-life Variables

The summary of results for quality-of-life variables will be presented separately for the DBTP and OLTP, unless otherwise noted. Summaries for the DBTP will be presented by treatment groups (evinacumab, placebo) containing patients from the quality-of-life analysis set. Summaries for the OLTP will be presented by all patients and by treatment group in DBTP (i.e.,

evinacumab, placebo), for patients in the quality-of-life analysis set. No formal inferential testing will be performed for either period. Summaries will be descriptive in nature.

The baseline value is defined as the last available measurement prior to the date of the first double-blind study treatment administration (applicable to measurement derivations during both DBTP and OLTP).

EQ-5D

Individual EQ-5D items

Responses for each one of the 5 EQ-5D items will be summarized by patient frequency and percentage at baseline and each post-baseline visit. Responses are defined by 4 levels, specifically reporting level 1 (no problems), level 2 (some problems) and level 3 (extreme problems), and level 4 (not answered).

EQ-5D utility score

The observed value and the change from baseline of the utility score will be summarized using mean, median, Q1, Q3, SD, minimum and maximum for each post-baseline visit. Cumulative distribution functions for the change in utility score from baseline will be displayed at post-baseline visits.

HADS

The analysis of data from HADS instrument will be performed on the HADS quality-of-life analysis set.

The total score is the sum of the two sub-scores of anxiety and depression. Descriptive statistics (mean, median, Q1, Q3, SD, minimum and maximum) of the observed total scores and the change from baseline observed total scores will be summarized by visit.

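### The exploratory objective asks for the effect of evinacumab on quality of life, but SAP 5.12 plans only by-arm descriptive summaries and no randomised, baseline-adjusted difference with an interval at week 24.

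*Protocol*

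**What the plan says.** Protocol 2.3, Other Objective, states the aim: "To assess the effect of evinacumab on quality of life using the EQ-5D and HADS QOL questionnaires". Protocol 4.2.4 lists two matching endpoints among the other endpoints: "Response of each EQ-5D item, index score, and change of index score from baseline through week 24" and "Response on Hospital Anxiety and Depression Scale (HADS) from baseline through week 48". The amendment history calls them exploratory. Protocol 10.4 gives no method of analysis for either scale.

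SAP 4.12 fixes the EQ-5D times: "Quality of life endpoints include response to each EQ-5D items at week 0 and week 24". Table 3 of the protocol schedules HADS at day 1 and weeks 24, 40 and 48.

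SAP 3.6 defines the analysis set as "all randomized patients who received any study treatment with a baseline and at least 1 post-baseline evaluation", and adds: "Treatment assignments for the DBTP are based on the treatment received (placebo or evinacumab".

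SAP 5.12 then limits the output: "No formal inferential testing will be performed for either period. Summaries will be descriptive in nature". For EQ-5D it says: "The observed value and the change from baseline of the utility score will be summarized using mean, median, Q1, Q3, SD, minimum and maximum". It adds item frequencies and cumulative distribution functions of the utility change. HADS total score and its change get the same summary statistics by visit. No between-arm difference, standard error, confidence interval or model appears for either scale.

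**The concern.** In a placebo-controlled trial the effect of a drug is a contrast between randomised arms, and the planned output stops one step short of it. The data for that contrast will exist. Both scales are taken at baseline and at week 24, patients and sites are blinded up to week 24 (protocol 7.6.1), and week-24 assessments come before the first open-label dose (Table 3 footnotes).

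Week 24 is also the only opportunity. From then on every patient receives evinacumab, and the later HADS forms are completed after patients have learned their lipid results. If the week-24 difference is not specified in advance, whoever reports on the objective must either rely on a crude comparison or choose a contrast after seeing the data. The crude comparison leaves out the randomisation strata and uses baseline only by subtraction.

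**Working it through.** **The plan's own figure.** The documents state no sample size or precision for EQ-5D or HADS. The only figure is 57 patients (38:19) for LDL-C in protocol 10.2: difference 38, SD 35, two-sided 0.05, 90% power. It reproduces. At 2:1, a two-sample t-test has 89.9% power with 42 patients and 91.9% with 45, and 45/(1 − 0.20) = 56.25, which becomes 57 at 2:1. The figure does not bear on quality of life, but it supplies two patient counts: 57 as a ceiling and 45 (30:15) after the planned losses.

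**Assumptions.** The documents give no SD and no baseline to week-24 correlation r for either scale. Results are therefore in units of the score SD, with r assumed. SDs are taken as equal at both times and in both arms.

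**Variance factors for the arm difference**, in units of SD² × (1/n₁ + 1/n₂):
- observed week-24 score: 1
- change score: 2(1 − r)
- ANCOVA on baseline: 1 − r²

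SAP 5.12 reports both observed values and changes, so the fair comparator is the smaller of the first two factors.

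| r | Observed | Change | ANCOVA | Better planned ÷ ANCOVA |
|---|---|---|---|---|
| 0.3 | 1 | 1.40 | 0.91 | 1/0.91 = 1.10 |
| 0.5 | 1 | 1.00 | 0.75 | 1/0.75 = 1.33 |
| 0.7 | 1 | 0.60 | 0.51 | 0.60/0.51 = 1.18 |
| 0.8 | 1 | 0.40 | 0.36 | 0.40/0.36 = 1.11 |

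The last column is the equivalent sample-size ratio. The gain is about 10-33% and peaks at r = 0.5.

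**95% half-width** = t × √(1/n₁ + 1/n₂) × √(variance factor). The square root of the sample-size term is 0.281 for 38:19 and 0.316 for 30:15. Degrees of freedom are N − 2 for the unadjusted comparisons and N − 3 for ANCOVA.

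| Patients | r | Observed | Change | ANCOVA |
|---|---|---|---|---|
| 38:19 | 0.3 | 0.56 | 0.67 | 0.54 |
| 38:19 | 0.5 | 0.56 | 0.56 | 0.49 |
| 38:19 | 0.7 | 0.56 | 0.44 | 0.40 |
| 30:15 | 0.3 | 0.64 | 0.75 | 0.61 |
| 30:15 | 0.5 | 0.64 | 0.64 | 0.55 |
| 30:15 | 0.7 | 0.64 | 0.49 | 0.46 |

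The ANCOVA column counts treatment and baseline only. The two strata terms would use two more degrees of freedom.

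**The case against.** The strongest reply is that the SAP is consistent with itself. Quality of life is an exploratory item, SAP 5.12 says openly that it is descriptive, and safety and other variables are handled the same way. No section promises an effect estimate. This stands, and it limits the point to an improvement. It does not rule the improvement out. The same SAP reports differences with confidence intervals for subgroups, with interaction significance for description only (5.7.1.2). It also gives descriptive p-values for other secondary endpoints (5.7.2.5) and compares the arms on baseline characteristics (5.1). An estimate with an interval is not a formal test.

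A reader might infer that, under this plan, an absence of visible difference could not be told apart from low precision. The documents do not support that. Arm counts, means and SDs are reported, and a crude difference and its interval follow from them. What is missing is the adjusted, as-randomised version, stated in advance.

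A reader might also measure the gain against change scores alone, which makes it look much larger when r is low. SAP 5.12 reports observed values too, and for r below 0.5 these are the more precise of the two.

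Three further limits stand:
- **The utility score is bounded and has a gap at the top.** Under SAP 10.5 the smallest departure from full health costs 0.036 + 0.081 = 0.117, so the score falls from 1 to at most 0.883. Item frequencies and distribution functions suit such a score, and a mean difference should sit beside them rather than replace them.
- **38:19 is a ceiling.** One missing item voids the utility score (SAP 4.12). The baseline EQ-5D cell in Table 3 also lacks the footnote marking assessments required of direct entrants from R727-CL-1628.
- **Grouping by treatment received is secondary.** It departs from randomisation only if someone is misdosed, and the ITT set also requires dosing.

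**Conclusion.** The point holds as a minor gap. Protocol 2.3 asks for an effect, and SAP 5.12 produces by-arm summaries from which only a crude, unadjusted, as-treated difference can be recovered. The benefit of adjustment is modest: about 10-33% more patients' worth of precision for an assumed r of 0.3-0.8. Even with adjustment the interval is wide, at about ±0.40-0.54 SD with 57 patients or ±0.46-0.61 SD with 45 evaluable (assumed r 0.3-0.7). As an illustration, with an assumed utility SD of 0.25 and r = 0.5, the half-width at 38:19 falls from about 0.25 × 0.56 = 0.14 to 0.25 × 0.49 = 0.12.

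The main value lies in naming one randomised contrast in advance at the only time it can be made; the gain in precision is secondary. A reader might extend the same model to HbA1c change at week 24. That was not examined here and forms no part of this conclusion.

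**What to change.** Add to SAP 5.12, for EQ-5D utility and the HADS scores at week 24:
- the LS mean difference, evinacumab minus placebo, with its 95% CI;
- from ANCOVA with treatment, the randomisation strata and the baseline score;
- by randomised arm, in patients with both baseline and week-24 data, with the number per arm shown;
- labelled descriptive, with no alpha claim.

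Keep the item frequencies and cumulative distribution functions for EQ-5D. State that the estimate is complete-case, and that HADS after week 24 cannot give a randomised comparison.

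The cost is a few lines of SAP text and one table from data already collected. The testing hierarchy does not change.

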3. HYPOTHESIS AND RATIONALE

3.1. Hypothesis

Blockade of ANGPTL3 with evinacumab will reduce LDL-C in patients with HoFH.

3.2. Rationale

3.2.1. Rationale for Study Design

This study is intended to demonstrate efficacy and safety of evinacumab in the treatment of HoFH. Diagnosis of HoFH will be based on either genotyping or clinical criteria. The genetic definition will include all individuals considered to be FH homozygotes, which is defined by the presence of the same mutation(s) in both LDLRs, Apo B, PCSK9 or LDLRAP1 alleles, or individuals considered to be compound heterozygotes, defined by the presence of different mutations in the same allele, or double heterozygotes, defined as mutations in different genes.

The percent change in LDL-C from baseline to week 24 will be the primary endpoint. LDL-C is an accepted surrogate endpoint for CV risk, and has repeatedly been used as the primary endpoint for approval of multiple other HoFH treatments. This study is designed as a placebo-controlled trial with the addition of evinacumab on top of patients' existing treatment regimens of maximally tolerated LMT, including lipid apheresis. This study will utilize a run-in period for those patients whose LMT regimen is not stable. This "add-on" design is appropriate because removal of any therapies from patients' existing treatment regimen will lead to an increase in LDL-C and possibly contribute to the serious CV sequelae seen in this severe disease with high CV risk.

The study consists of 4 periods: run-in (for patients whose background medical LMT has not been stable for at least 4 weeks prior to screening or whose apheresis settings and/or schedule have not been stable for at least 8 weeks prior to screening), screening, double-blind treatment, and open-label treatment. In the 24-week double-blind treatment period (DBTP), patients will receive evinacumab 15 mg/kg IV Q4W or matching placebo IV Q4W.

In order to provide additional safety, PK, and long term efficacy information on evinacumab in this rare patient population, after completion of the DBTP, all patients will enter a 24-week open-label treatment period (OLTP). During the OLTP portion of the study, all patients, regardless of treatment assignment in the DBTP, will receive evinacumab 15 mg/kg IV every month.

3.2.2. Rationale for Dose Selection

The 15 mg/kg IV dose is selected based on safety and the substantial LDL-C reduction observed in HoFH patients in study R1500-CL-1331. The higher dose regimen of 20 mg/kg IV Q4W demonstrated favorable tolerability when given as an 8-week treatment in otherwise healthy subjects (R1500-CL-1321) and so the 15 mg/kg IV Q4W regimen is expected to also demonstrate favorable tolerability, because the evinacumab exposure within each dosing interval is expected to be lower and the accumulation of serum concentration with a monthly dosing frequency is predicted to be minimal. From an efficacy perspective, the 15 mg/kg IV dose has previously demonstrated evinacumab concentrations above 100 mg/L for approximately 4 weeks; an exposure threshold associated with target saturation and maximal effect on TG reduction (R1500-CL-1321 and R1500-HV-1214). Based on these PK/PD data, combined with the efficacy data from the proof-of-concept study in HoFH (R1500-CL-1331), 15 mg/kg IV is expected to maintain target saturation and thereby to provide maximal benefit during the monthly dosing interval.

3.2.3. Risk/Benefit Assessment

Patients with HoFH have extremely high LDL-C levels, are far from their target level and will require significant reductions to get to their goal. Despite the approval of newer treatments including evolocumab, lomitapide and mipomersen, the need for more intensive therapies remains. Evinacumab could be a new addition to the armamentarium of LMT that could contribute to lowering the LDL-C of patients with HoFH. In study R1500-CL-1331, evinacumab demonstrated a mean percent reduction from baseline of 49.2% (n=9) at week 4, with a duration of effect of at least 10 weeks after a 15 mg/kg IV dose (n=7). A peak mean reduction of 52.1% was observed at week 6. Three patients in the study are homozygous for null mutations in the LDLR. Treatment with evinacumab in these difficult-to-treat patients reduced LDL-C by an average of 37.3% at week 4 with peak reductions up to 59.5%. Based on these data, it is expected that the addition of evinacumab to existing treatments will lead to significant LDL-C reductions in the HoFH

population. The body of evidence from the statin literature shows that the relationship between LDL-C reduction and CV event reduction is approximately linear and for every 1 mmol/L (38.7 mg/dL) reduction in LDL-C there is a corresponding 22% risk reduction in CV events ([Cholesterol Treatment Trialists' Collaboration 2010](#)). Moreover, the results from the recent outcomes trials with ezetimibe (IMPROVE-IT [[Cannon 2015](#)]), alirocumab (ODYSSEY OUTCOMES [[Steg 2018](#)]) and evolocumab (FOURIER [[Sabatine 2017](#)]) reinforce this concept, providing additional evidence for the relationship between LDL-C lowering and reductions in CV events and the importance for patients to achieve their target LDL-C. Within the context of this study in the HoFH patient population, additional reduction in LDL-C may get patients closer their LDL-C target, which could translate into significant benefits.

It is also expected that treatment with evinacumab will be well tolerated and have an acceptable safety profile. The accumulated safety information from the completed and ongoing clinical studies is marked by the absence of any important identified risks. There are potential risks that include systemic hypersensitivity reactions, immunogenicity, and embryofetal toxicity. These risks will be managed through careful patient selection and monitoring. For the potential embryofetal toxicity risk, there is a strict risk mitigation plan, including requirements for consistent use of contraception for sexually active male study participants and sexually active female study participants of child-bearing potential.

Patients entering this study should be on a background statin, ezetimibe, and a PCSK9 inhibitor, unless they have a documented history of tolerability issues, lack of efficacy, or other reason. Patients should be on these lipid lowering drugs because of the above mentioned proven CV risk reduction demonstrated in recent CV outcomes trials (ODYSSEY OUTCOMES, FOURIER, IMPROVE-IT). There are 2 PCSK9 inhibitors on the market; evolocumab is approved for use in patients with HoFH in most countries, and alirocumab is currently being evaluated in a double-blind placebo-controlled study in patients with HoFH (study R727-CL-1628, ODYSSEY HoFH). Patients entering this study may be taking either evolocumab or alirocumab. Patients who complete study R727-CL-1628 (ODYSSEY HoFH) with alirocumab are permitted to participate in this study and will continue to receive alirocumab as part of their background LMT. The concurrent use of evinacumab with alirocumab is considered to have an acceptable benefit/risk profile because it could be beneficial and is not considered to pose any safety concerns.

Evinacumab and alirocumab have different mechanisms of action and concomitant administration of both agents is not expected to perturb the action of the other. Rather, their distinct mechanisms of action are anticipated to complement each other to lower LDL-C since they work at different sites of action.

The safety profile of each agent is considered acceptable and the concurrent use of the 2 agents together is not expected to augment or exacerbate potential adverse events (AEs). Concomitant use of evinacumab and evolocumab was found to have an acceptable safety profile in 4 patients in the R1500-CL-1331 study, a study evaluating evinacumab in 9 patients with HoFH (details of the study are provided in the evinacumab Investigator's Brochure and the Introduction [[Section 1](#)]). No safety signals or adverse effects related to the concomitant use of both agents have been observed. The safety of the use of evinacumab along with alirocumab will be carefully monitored in this study. Safety monitoring will include ongoing reviews by an unblinded Independent Data Monitoring Committee (IDMC), by the sponsor's blinded safety monitoring team (SMT), and by the blinded clinical study team. If significant safety trends or findings are identified by either the

IDMC or the sponsor's blinded study team or SMT, they will be escalated and appropriately evaluated to understand the best course of action.

From the perspective of PK drug-drug interactions, co-administration of evinacumab, alirocumab, and the other possible background LMT (statin, ezetimibe, etc) is not expected to result in drug-drug interactions with each other or other drugs. Evinacumab and alirocumab are both eliminated via a combination of non-saturable, linear, proteolytic degradation and saturable, non-linear target-mediated clearance. The 2 molecules bind to different targets and the target-mediated pathways are entirely independent. Neither evinacumab nor alirocumab are a cytokine or cytokine modulator; therefore, it is not anticipated to interact directly or indirectly with cytochrome P450 enzymes, other drug metabolizing enzymes or drug transporters, which are known to influence the disposition of statins. Conversely, the PK of evinacumab is not expected to be impacted by statins, due to its elimination pathways.

Indeed, the concomitant administration of 2 fully human monoclonal antibodies may be a new treatment paradigm in CV medicine, but not uncommon in other therapeutic areas such as autoimmune disease or oncology. Experience in those areas has demonstrated the use of multiple biologic agents to be acceptable from a safety and tolerability perspective.

For the reasons stated above, the benefit/risk profile for the concurrent use of evinacumab and PCSK9 inhibitor antibodies or the use of evinacumab in the absence of a PCSK9 inhibitor antibody as part of the background LMT is considered favorable.

